### 9.2. Sample Size and Power Considerations

Sample size calculations were based on the following assumptions:

- 2-sided alpha level of 5%
- treatment difference (delta) of 0.3 in PBVC
- standard deviation of 0.8

Under the above assumptions 252 patients enrolled for 0.6 mg and placebo (126 per arm) will provide 84% power to detect a statistically significant result for 0.6 mg laquinimod arm comparison to placebo. To adjust for the anticipated 10% dropouts, the sample size was increased to 280 patients. Adding 95 patients on 1.5 mg yields a total of 375 patients.

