3.3. Sample Size and Power Considerations

Sample size calculations were based on the following assumptions:

- 2-sided alpha level of 5%
- treatment difference (delta) of 0.3 in PBVC
- standard deviation of 0.8
- drop-out date of 10%

Under the above assumptions in order to reach power of 80%, 125 patients per arm should be enrolled. Since initially, this study was planned to have 3 treatment arms, the original sample size was 375 patients. Although, the enrollment to 1.5 mg laquinimod arm was stopped as specified in Section 3.1 and included 95 randomized patients, the Sponsor decided to continue enrollment to the laquinimod 0.6 mg and placebo arms until the total sample size reaches the initially planned 375 patients. This will result in 140 patients per arm (lauqinimod 0.6 mg/placebo) which provides 84% power.

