5.3. Multiple Comparisons and Multiplicity

The overall significant level for this study is 5%, using two-tailed tests and/or two-sided confidence intervals with 95% confidence level. In order to protect the study from type-I error inflation, the secondary endpoints will be interpreted inferentially only if a statistically significant treatment effect is detected in the primary analysis. Type-I error will be further controlled by employing the Hierarchical Approach, (i.e. each secondary endpoint will be analyzed only in case the preceding endpoint will have a p-value less or equal to 0.05) according to the following order:

1. Time to CDP as measured by EDSS

2. Time to CDP event as measured by EDSS or T25FW
3. Change from baseline to week 48 in the T25FW test
4. The number of new T2 lesions at week 48

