7.2. Primary Efficacy Variable and Analysis

The primary efficacy variable for this study is BA as measured by the PBVC from baseline to week 48. This endpoint will be analyzed using the mITT1 population and will include all the assessments done up to one month after the last dose of the study drug (all the following assessments will be excluded from this analysis). BA will be analyzed using baseline-adjusted repeated measures analysis of covariance (ANCOVA- SAS® PROC MIXED) in which 1 contrast will be constructed in order to compare between laquinimod 0.6 mg and placebo.

The model will be comprised from the treatment group as a class variable (2 levels). In addition to the treatment group, week (categorical, 2 levels), treatment by week interaction, normalized brain volume at baseline, natural logarithm of T2 lesion volume at baseline, and CGR will be used as covariates. Additionally, week (categorical) will be specified as a repeated effect and unstructured (UN) correlation matrix will be used to model intra-subject correlation. In case a convergence issue will arise using the UN correlation matrix, (1) AR1 or (2) Compound Symmetry (CS) will be used to enable model convergence (in this order). The SAS code for this analysis is as follows:

```
PROC MIXED;
  CLASS SUBJID ARM WEEK CGR;
  MODEL BA=ARM WEEK ARM*WEEK NBVBASE LT2BASE CGR / SOLUTION CL;
  REPEATED WEEK / TYPE=UN SUBJECT=SUBJID R RCORR;
  ESTIMATE 'Laq 0.6 to Plb on Week 48' ARM 1 -1 ARM*WEEK 0 1 0 -1 / CL;
  LSMEANS ARM*WEEK / PDIFF CL;
  WHERE ARM in ('Laquinimod 0.6 mg', 'Placebo');
RUN;
```

In addition, mean values of the BA as measured by the PBVC from baseline to weeks 24 and 48 will be summarized using descriptive statistics.

Since for the purpose of this analysis scans of patients who discontinue the study after week 36 are considered as scans at week 48 (see Section 5.5), PBVC measures from the scans of these patients will be presented also separately using descriptive statistics.

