7.4.3. Change from baseline to week 48 in the T25FW test

Change from baseline in the T25FW test at week 48 will be analyzed using the mITT2 population and will include all the assessments done up to seven days after the last dose of the study drug (all the following assessments will be excluded from this analysis). Since this variable might not follow normal distribution, the ranked values of this measurement will be defined and analyzed using baseline adjusted repeated measures ANCOVA (SAS® PROC MIXED) in which 1 contrast will be constructed in order to compare between laquinimod 0.6 mg and placebo. In addition to treatment group, T25FW test at baseline, week (categorical, 4 levels), treatment by week interaction and CGR will be used as covariates. Additionally, week (categorical) will be specified as a repeated effect and unstructured (UN) correlation matrix will be used to model intra-subject correlation. In case a convergence issue will arise using the UN correlation matrix, (1) AR1 or (2) Compound Symmetry (CS) will be used to enable model convergence (in this order). Due to the fact that the ANCOVA model will use ranked values and not the actual

changes in the T25FW, Hodges-Lehmann estimates will be used in order to present the magnitude of the treatment effect and the corresponding two sided 95% confidence limit.

The SAS code for defining ranked values and performing this analysis is as follows:

1. Ranked values assignment:

```
PROC RANK OUT=RANKED;
  VAR CHANGE T25BASE;
  RANKS CHANGERANK T25BASERANK;
  WHERE ARM in ('Laquinimod 0.6 mg', 'Placebo');
  RUN;
```

2. Repeated measures ANCOVA model:

```
PROC MIXED DATA=RANKED;
  CLASS SUBJID ARM WEEK CGR;
  MODEL CHANGERANK=ARM WEEK ARM*WEEK T25BASERANK CGR;
  REPEATED WEEK / TYPE=UN SUBJECT=SUBJID R RCORR;
  ESTIMATE 'Laq 0.6 to Plb' ARM 1 0 -1 ARM*WEEK 0 0 0 1 0 0 0 -1 / CL;
  LSMEANS ARM*WEEK / PDIFF CL;
  RUN;
```

3. HL estimates:

```
PROC NPAR1WAY HL;
  CLASS ARM;
  VAR CHANGE;
  WHERE WEEK=48 and ARM in ('Laquinimod 0.6 mg', 'Placebo');
  RUN;
```

In addition, actual values of T25FW and changes from baseline to each visit will be summarized using descriptive statistics.

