When the study is completed, actual values of T25FW and changes from baseline to each visit will be summarized using descriptive statistics to include both part A and part B. Also, the changes from baseline to each visit will be analyzed using similar statistical methodology as presented in this section for changes from baseline to week 48 in T25FW test.

7.4.4. The number of new T2 lesions at week 48

The number of new T2 lesions at week 48 compared to baseline will be analyzed using the mITT1 population and will include all the assessments done up to one month after the last dose of the study drug (all the following assessments will be excluded from this analysis). This analysis will be performed using baseline adjusted negative binomial regression model (SAS® PROC GENMOD) in which 1 contrast for comparing laquinimod 0.6 mg to placebo will be constructed. In addition to the treatment group, the natural logarithm of T2 lesion volume at baseline, age at baseline and CGR will be used as covariates. The SAS code for this analysis is as follows:

```
PROC GENMOD;
  CLASS ARM CGR;
  MODEL T2LES=ARM LT2BASE AGE CGR/ DIST=NB LINK=LOG TYPE3;
```

```
LSMEANS ARM/ CL;  
ESTIMATE 'Laq 0.6 to Plb' ARM 1 -1 / ESTIMATE=EXP;  
WHERE ARM in ('Laquinimod 0.6 mg', 'Placebo');  
RUN;
```

In addition, the number of new T2 lesions at week 48 will be summarized using descriptive statistics.

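### For PBVC the two fallback covariances, AR(1) then CS, are one equal-variance model at two visits; a heterogeneous-variance or robust fallback should replace them (minor)

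*SAP*

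**What the plan says.** SAP 7.2 fits PBVC in PROC MIXED with week as a two-level factor, an unstructured (UN) covariance and a single contrast at week 48. If UN does not converge, "1) AR1 or (2) Compound Symmetry (CS) will be used to enable model convergence (in this order". Protocol 9.6.4.1 has the same rule. The SAP code requests model-based standard errors; there is no EMPIRICAL option.

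The rule recurs elsewhere. SAP 7.4.3 (T25FW, analysed on ranks, four visits) opens it with "In case a convergence issue will arise using the UN correlation matrix". SAP 7.5.15 (SDMT) repeats it. SAP 7.5.14 (9HPT), 7.5.16 (LCVA) and 7.5.17 (MSWS-12) inherit it by reference. For all five measures the SAP adds a repeat at study completion on Parts A and B together; in SAP 7.4.3, "the changes from baseline to each visit will be analyzed using similar statistical methodology as presented in this section".

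On error control, SAP 5.3 states: "The overall significant level for this study is 5%, using two-tailed tests". It makes significance on PBVC the condition for interpreting the four secondary endpoints.

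**The concern.** A pre-specified fallback should protect the test when the first choice fails. This one gives up what keeps the UN test valid, a separate variance at each visit. PBVC accumulates from baseline, so one would expect a wider spread at week 48 than at week 24. A pooled variance then understates the standard error at week 48, the only visit tested. A false positive there would also open the secondary hierarchy. SAP 7.3 has no sensitivity analysis of the covariance structure that would show the problem. In addition, the ordered list offers no real second option for PBVC.

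**Working it through.** **Inputs.** From Protocol 9.2: "treatment difference (delta) of 0.3 in PBVC", "standard deviation of 0.8" and "252 patients enrolled for 0.6 mg and placebo (126 per arm) will provide 84% power". The visit to which the SD refers is not stated; I read it as week 48. PBVC is measured at week 24 and at week 48 or early termination (Protocol 6.4.1). The documents give no week-24 SD and no between-visit correlation, so both are assumed below.

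**1. The plan's own figure.** SE = 0.8 × √(2/126) = 0.1008. Then 0.3/0.1008 − 1.96 = 1.016, and Φ(1.016) = 84.5%. The stated 84% reproduces (84.3% with the noncentral t).

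**2. The two fallbacks coincide.** AR(1) sets the correlation at lag k to ρ^k; CS sets every correlation to ρ. With two visits the only lag is 1, so both give σ² × [[1, ρ], [ρ, 1]]: two parameters, one variance. UN has v(v+1)/2 = 3. CSH and ARH(1) at two visits also have three (two variances, one correlation) and are UN in another parameterisation.

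**3. Size of the week-48 test under the fallback.** With complete data the model-based variance at week 48 is (SD24² + SD48²)/2. With r = SD24/SD48, the standard error is f = √((1 + r²)/2) times the correct one, and the two-sided size is 2 × [1 − Φ(1.96 f)].

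| Assumed SD24 (SD48 = 0.8) | r | f | size |
|---|---|---|---|
| 0.40 | 0.50 | 0.791 | 12.1% |
| 0.52 | 0.65 | 0.843 | 9.8% |
| 0.60 | 0.75 | 0.884 | 8.3% |
| 0.64 | 0.80 | 0.906 | 7.6% |
| 0.72 | 0.90 | 0.951 | 6.2% |
| 0.80 | 1.00 | 1.000 | 5.0% |
| 0.88 | 1.10 | 1.051 | 3.9% |

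Solving backwards, a size of 6-10% needs r between about 0.64 and 0.92.

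**4. Check with missing scans.** A REML simulation (not in SAS) used 140 patients per arm, 10% of week-48 scans removed at random, an assumed correlation of 0.6 and 2,500 runs per scenario. The fallback rejected in 10.4%, 7.5%, 6.5%, 4.3% and 3.7% of runs at r = 0.6, 0.75, 0.9, 1.0 and 1.1. UN rejected in 4.3-5.4% and converged in all 5 × 2,500 = 12,500 fits. These fits had arm-by-week means only, without the baseline covariates or CGR.

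**5. Part B.** T25FW, 9HPT, SDMT and MSWS-12 are taken every 12 weeks. To week 144 that is 144/12 = 12 visits, and UN needs 12 × 13/2 = 78 covariance parameters. LCVA is taken every 24 weeks: 144/24 = 6 visits and 6 × 7/2 = 21 parameters. The schedule footnotes expect few patients beyond week 120. A 12-visit UN ties the last visit to the 11 earlier ones as well as to the arm means. If only about 12 or fewer patients reach that visit, no information is left for its residual variance and UN cannot be estimated.

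**The case against.** The strongest reply is that the trigger hardly exists for the primary endpoint. UN has one parameter more than the fallback, with about 280 patients, and it never failed in simulation. That stands, subject to the simpler mean model used in the check.

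A reader might infer that the week-48 test is planned at 6-10% instead of 5%. The documents do not support that. The figure applies only if the fallback is used, and only for an assumed range of SD ratios. Other ratios give more than 10%, exactly 5%, or less than 5%.

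A reader might also put a large number on Part B. Take a visit variance of 1 + (k × week/48)² with k from 0.5 to 1.5, and patient numbers falling from 280 to about 33 by week 120. Week-120 tests would then run at about 15-28% on raw values. Both k and the patient numbers are assumptions. T25FW and 9HPT are analysed on ranks, whose variance is bounded; a similar scenario on pooled ranks gave about 9-14%. LCVA has about half as many visits as the other four measures.

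Finally, SAP section 1 describes the Part B analyses as exploratory, and none is in the SAP 5.3 hierarchy. That also stands: an inflated late-visit p-value there changes no confirmatory conclusion. None of this defends listing the same model twice, or dropping visit-specific variances when UN fails.

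**Conclusion.** The structural defect is certain: for PBVC the two fallbacks are one model, and it imposes equal variances with no robust standard error. Its effect is conditional. If the fallback were used and SD24 were about 0.65-0.9 of SD48, the week-48 size would be about 6-10%. That ratio is plausible for a cumulative change but appears nowhere in the documents. The primary result is unlikely to be affected, because UN should almost always converge.

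The realistic place for the rule to operate is the exploratory Part B each-visit models. Late-visit tests there would be anti-conservative if variance grows with time, less so for the ranked T25FW and 9HPT. The documents do not allow a figure. Severity: minor.

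**What to change.** Amend the fallback list in Protocol 9.6.4.1 and in SAP 7.2, 7.4.3 and 7.5.14-7.5.17.

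- **Three or more visits:** heterogeneous Toeplitz (TOEPH), then ARH(1), then CSH.
- **Two-visit PBVC:** first refit the same covariance with other starting values, or as CSH or ARH(1). Only if that fails, use CS with empirical (sandwich) standard errors.

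The cost is wording. No new data are needed, and results are unchanged wherever UN converges. One small downside remains: sandwich errors correct the standard error, but not bias in the estimate when missing week-48 scans depend on the week-24 value. An ANCOVA at week 48 alone is not preferred, because it drops mITT1 patients who have only a week-24 scan.

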7.5.15. Change from baseline to week 48 in Symbol Digit Modalities Test (SDMT)

Change from baseline to week 48 in SDMT score will be analyzed for mITT2 population using baseline adjusted repeated measures analysis of covariance (ANCOVA SAS® PROC MIXED) in which 1 contrast will be constructed in order to compare between laquinimod 0.6 mg and placebo. The model will be comprised from the treatment group as a class variable (2 levels). In addition to the treatment group, week (categorical, 4 levels), treatment by week interaction, SDMT at baseline, and CGR will be used as covariates. Additionally, week (categorical) will be specified as a repeated effect and unstructured (UN) correlation matrix will be used to model intra-subject correlation. In case a convergence issue will arise using the UN correlation matrix, (1) AR1 or (2) Compound Symmetry (CS) will be used to enable model convergence (in this order). The SAS code for this analysis is as follows:

```
PROC MIXED;
  CLASS SUBJID ARM WEEK CGR;
  MODEL CSDMT=ARM WEEK ARM*WEEK SDMTBASE CGR / SOLUTION CL;
  REPEATED WEEK / TYPE=UN SUBJECT=SUBJID R RCORR;
  ESTIMATE 'Laq 0.6 to Plb' ARM 1 -1 ARM*WEEK 0 0 0 1 0 0 0 -1 / CL;
  LSMEANS ARM*WEEK / PDIFF CL;
  WHERE ARM in ('Laquinimod 0.6 mg', 'Placebo');
RUN;
```

In addition, actual values of the SDMT score and changes from baseline to each visit will be summarized using descriptive statistics.

When the study is completed, actual values of SDMT and changes from baseline to each visit will be summarized using descriptive statistics to include both part A and part B. Also, the changes from baseline to each visit will be analyzed using similar statistical methodology as presented in this section for changes from baseline to week 48 in SDMT test.

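### The primary PBVC model gives baseline brain volume and log T2 lesion volume one slope for both visits; if their effect grows by week 48, some precision is lost there, but nothing else.

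*SAP*

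**What the plan says.** The code in SAP Section 7.2 reads "MODEL BA=ARM WEEK ARM*WEEK NBVBASE LT2BASE CGR / SOLUTION CL". Brain volume, log T2 lesion volume and country/region are main effects, and treatment is the only term crossed with week. The prose in 7.2 and protocol Section 9.6.4.1 list the same terms, so this is the intended model and not a coding slip. Week has two levels (24 and 48), PBVC at each is measured from the baseline scan, and the within-patient covariance is unstructured. The treatment contrast is taken at week 48.

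No other analysis crosses either covariate with week. The interaction checks in 7.2 concern treatment by covariate and treatment by region. The sensitivity analyses in 7.3 change the population, drop covariates or add them. The by-gender PBVC model in 7.5.21 crosses gender with week but leaves the two MRI covariates as main effects.

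The sample size (SAP 3.3, protocol 9.2) assumes "2-sided alpha level of 5" percent, "treatment difference (delta) of 0.3 in PBVC" and "standard deviation of 0.8". Neither document claims a gain from covariate adjustment.

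**The concern.** The week-48 value contains the change up to week 24. Protocol Section 1.1.1.3 describes atrophy as a rate, adjusted for baseline brain volume. If a baseline covariate predicts that rate, its coefficient should be larger over 48 weeks than over 24. A model with one slope has to compromise, and generalized least squares usually weights the less variable visit more, which is likely to be week 24. The fitted slope is then too small for week 48, and covariate-related variation that could have been removed stays in the residual.

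What is at stake is the precision of the one powered endpoint. Under SAP Section 5.3 that endpoint is also the gate to inferential interpretation of the secondary endpoints.

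**Working it through.** **The plan's own figure.** With 126 per arm and SD 0.8, SE = 0.8 × √(2/126) = 0.1008 and 0.3/0.1008 = 2.976. Power is Φ(2.976 − 1.960) = 84.5% (84.3% by the t distribution). This reproduces "252 patients enrolled for 0.6 mg and placebo (126 per arm) will provide 84% power". The dropout step also reproduces: 252/0.9 = 280.

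**Assumed inputs.** The documents give none of these:
- R-squared of the covariates at week 48: 10% or 20%, treating 0.8 as the unadjusted SD.
- Ratio of week-24 to week-48 slope: 0.5, 0.75 or 1.
- Week-24 SD: 0.45 to 0.80.
- Correlation between the two visits: 0.4 to 0.8.

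**Formulas.** The two covariates are treated as one standardized score.
- True slopes: b48 = √R² × 0.8 and b24 = ratio × b48.
- Residual covariance with the correct slopes: E = S − bb′, where S is the total covariance and b = (b24, b48)′.
- With a common slope c, the unstructured matrix absorbs the misfit: V = E + (b − c)(b − c)′.
- The fitted c is w·b24 + (1 − w)·b48, with w = (V48 − V24,48)/(V24 + V48 − 2V24,48), iterated until c is stable.
- Variance ratio at week 48: 1 + (b48 − c)²/E48.

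**One case in full** (R-squared 10%, ratio 0.5, week-24 SD 0.65, correlation 0.6):
- b24 = 0.1265, b48 = 0.2530, E48 = 0.64 × 0.9 = 0.576.
- At convergence V24 = 0.4079, V48 = 0.5839 and V24,48 = 0.2766, so w = 0.3072/0.4385 = 0.70.
- c = 0.70 × 0.1265 + 0.30 × 0.2530 = 0.164, which is 65% of b48.
- Excess variance is (0.2530 − 0.1644)² = 0.0079, and 0.0079/0.576 = 1.4%. That is worth 126 × 0.014 ≈ 1.7 patients per arm.
- Power at 126 per arm is 87.6% with the common slope and 88.1% with by-week slopes.

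**Full assumed range:**

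| R-squared | Slope ratio | Common slope as share of b48 | Excess week-48 variance |
|---|---|---|---|
| any | 1 | 100% | 0 |
| 10% | 0.75 | 68–89% | 0.1–1.1% |
| 10% | 0.5 | 36–80% | 0.4–4.5% |
| 20% | 0.5 | 39–86% | 0.5–9.4% |

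Shares below 50% arise when the covariance between visits exceeds the week-24 variance, which makes the weight on week 48 negative. For example, week-24 SD 0.60 with correlation 0.8 at R-squared 10% gives w = 1.04, a share of 48% and an excess of 3.0%.

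At ratio 0.5, by-week slopes raise power from between 86.6% and 87.9% to 88.1% at R-squared 10%, and from between 88.9% and 91.3% to 91.4% at 20%.

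**Simulation check** (140 per arm, 10% missing at week 48, 1,500 runs per scenario, ratio 0.5, week-24 SD 0.65, correlation 0.6). Week-48 SEs for common slope, by-week slope and no covariate were 0.0946, 0.0939 and 0.0989 at R-squared 10%, and 0.0903, 0.0889 and 0.0991 at 20%. The variance ratios are (0.0946/0.0939)² = 1.015 and (0.0903/0.0889)² = 1.032, against 1.014 and 1.026 from the formula. The mean estimate was 0.302 for a true 0.30, and type I error was 4.9%.

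**The case against.** The strongest reply is that the growing slope is assumed. Nothing in the documents shows that either covariate's coefficient rises between visits, let alone doubles. The remark in protocol 1.1.1.3 gives no coefficient, and that section also says the time course of laquinimod's effect on PBVC is not clearly defined. With equal slopes nothing is lost. This stands, and it is why the point is conditional.

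It is also true that the specified model is valid, did at least as well as no covariates in every simulated scenario, and is the protocol's own. On that view, adding interactions is a matter of preference. That stands in part: the change is optional, but it gives the covariates their proper use at little cost.

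A reader might infer that the primary result is biased, that type I error is inflated, or that the power claim fails. None of these follows. Randomization protects the contrast, and the 84% rests on an SD of 0.8 with no covariate gain claimed.

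A reader might also carry the argument to other repeated-measures models of the same shape, such as "MODEL CHANGERANK=ARM WEEK ARM*WEEK T25BASERANK CGR" for T25FW and "MODEL CSDMT=ARM WEEK ARM*WEEK SDMTBASE CGR / SOLUTION CL" for SDMT, or to MSWS-12, 9HPT and LCVA. The documents do not support that. These are performance or patient-reported scores, and a baseline coefficient for change in such a score partly reflects regression to the mean, which need not grow with time. T25FW and 9HPT are also analysed as ranks. No loss has been calculated for any of them, and with four visit levels the T25FW and SDMT models would need three extra parameters per covariate.

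Country/region is uncrossed with week too. No calculation was made for it, so no change is proposed.

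**Conclusion.** The concern holds as a minor, conditional point about precision on PBVC. The single-slope restriction is certain from the text. That it costs anything depends on the covariates predicting PBVC and on their slopes being larger at week 48, which is plausible for a cumulative outcome but not shown.

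Under the assumed ranges the excess week-48 variance runs from zero with equal slopes to about 0.4–4.5% at R-squared 10% with a half-size week-24 slope, and about 0.5–9% at 20%. In power this is at most about 1.5 points (88.1 − 86.6) and 2.5 points (91.4 − 88.9), both on top of a figure already above the stated 84%. The claim that the slope doubles, and that a fixed share of the adjustment is therefore lost, goes beyond what the documents can support.

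**What to change.** Before unblinding, add NBVBASE*WEEK and LT2BASE*WEEK to the MODEL statement in SAP 7.2 and to the PBVC repeats that keep these covariates: the per-protocol and additional-covariate analyses in 7.3 and the by-gender PBVC model in 7.5.21. Amend the prose in 7.2 to match, and list the change in SAP Section 12, because the model is specified in protocol 9.6.4.1. SAP 3.5.2 keeps the codes blinded until the SAP is approved and the Part A database is locked, so the change can be made within that process.

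The cost is two extra parameters and a documented departure from the protocol model. If the sponsor prefers to keep the protocol model as primary, the by-week version can be a pre-specified sensitivity analysis in 7.3, though the primary test then gains nothing.

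Leave the T25FW, SDMT, MSWS-12, 9HPT and LCVA models as they are. SAP 7.5.16 defines the LCVA analysis by reference to 7.2, so it needs a sentence saying that the new terms do not carry over.

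### The primary PBVC model leaves out age at baseline; adding it before unblinding would be a free improvement of unknown, possibly zero, size

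*SAP*

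**What the plan says.** SAP 7.2 specifies the primary repeated-measures model as "MODEL BA=ARM WEEK ARM*WEEK NBVBASE LT2BASE CGR / SOLUTION CL". Besides treatment, week and their interaction, it adjusts for baseline normalized brain volume, log baseline T2 lesion volume and country/region (CGR). Protocol 9.6.4.1 has the same list. Neither document says why age is absent.

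Age appears elsewhere in the SAP:

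- Section 6.3 summarises it as a continuous baseline variable. Eligible patients are 25 to 55 years old (Protocol 4.1).
- The Cox models for time to CDP by EDSS (7.4.1) and by EDSS or T25FW (7.4.2) include it.
- The new-T2-lesion model (7.4.4) includes it: "the natural logarithm of T2 lesion volume at baseline, age at baseline and CGR will be used as covariates".
- Section 7.5.16 analyses low contrast visual acuity by the primary method and adds age to that model.
- Section 7.3 names age for PBVC, but only as a candidate in a sensitivity analysis, to be used if the 0.6 mg and placebo arms differ on it at p≤0.05.

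The sample size rests on PBVC alone. Protocol 9.2 assumes a "treatment difference (delta) of 0.3 in PBVC" and a "standard deviation of 0.8", and states that "252 patients enrolled for 0.6 mg and placebo (126 per arm) will provide 84% power". SAP 5.3 makes PBVC the gatekeeper: the secondary endpoints are interpreted inferentially only if it is significant.

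**The concern.** In a randomised comparison, a prespecified baseline covariate that predicts the outcome narrows the confidence interval for the treatment contrast without biasing it. The SAP treats age as worth adjusting for in three of its four secondary analyses, and adds it when the primary method is applied to another outcome, yet leaves it out of the primary analysis itself.

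SAP 7.3 does not fill the gap. Its trigger is a significance test of baseline balance. Under randomisation age will meet p≤0.05 about 5% of the time, and meeting it says nothing about whether age predicts PBVC. Even then, age enters only a sensitivity result.

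What is at stake is some possible precision on one contrast. That contrast carries the trial's only power calculation and opens or closes the whole secondary hierarchy.

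**Working it through.** **Inputs.** Two-sided alpha 0.05, delta 0.3, SD 0.8 and 126 evaluable per arm (Protocol 9.2). Enrolment is 140 per arm (SAP 3.3) with 10% dropout. No correlation between age and PBVC appears in either document, so the share of residual variance explained by age, R², is an assumption. Here it means the share left over after brain volume, T2 volume and CGR.

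**Reproducing the plan's figures.**

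- Dropout: 252 / 0.90 = 280, and 140 × 0.90 = 126 per arm. Both agree with the plan.
- Standard error: 0.8 × √(2/126) = 0.1008. Noncentrality: 0.3 / 0.1008 = 2.976.
- Power with 250 degrees of freedom (noncentral t): 84.3%. The normal approximation gives 84.5%. The stated 84% reproduces with no covariate in the calculation.

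**Adding age.** The adjusted SD is 0.8 × √(1 − R²). The equivalent sample size per arm is 126 / (1 − R²).

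| Assumed R² | Adjusted SD | Noncentrality | Power | Equivalent n per arm |
|---|---|---|---|---|
| 0 | 0.800 | 2.976 | 84.3% | 126 |
| 0.02 | 0.792 | 3.007 | 85.0% | 128.6 |
| 0.05 | 0.780 | 3.054 | 86.0% | 132.6 |
| 0.10 | 0.759 | 3.137 | 87.8% | 140 |

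**Cost if age adds nothing.** One degree of freedom, 249 instead of 250. Power falls by about 0.001 percentage points and still rounds to 84.3%.

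**Reading the range.** R² = 0.10 needs a partial correlation of √0.10 ≈ 0.32. At a partial correlation of 0.10 (R² = 0.01) the normal-approximation power moves only from 84.5% to 84.9%. At 0.20 (R² = 0.04) it reaches 86.0%.

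**Simplification.** Like the plan's own calculation, this is a two-sample comparison at week 48. It ignores any information that the mixed model borrows from week 24.

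**The case against.** The strongest objection is that the gain exists only if age predicts week-48 PBVC beyond the covariates already in the model, and nothing in the documents shows that it does. Protocol 1.1.1.3 supports adjusting for baseline brain volume and does not mention age. Using age for EDSS progression or lesion counts does not establish that it predicts atrophy. The 25 to 55 age limit, and any overlap between age and baseline brain volume, would shrink whatever gain there is. This stands: zero is as compatible with the documents as 10%.

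Consistency also cuts both ways. The other atrophy models omit age too: thalamic volume, cortical thickness, white matter volume and cervical cord area (SAP 7.5.8 to 7.5.11). PBVC therefore matches its own family of endpoints. Protocol Amendment 01 revisited age, making it continuous in the CDP models and adding it to the T2-lesion model, so covariates may have been chosen endpoint by endpoint. A reader might infer an oversight or an internal contradiction; the documents support neither.

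A reader might also infer that the trial is underpowered without age. It is not: 84% reproduces without any covariate and exceeds the 80% that SAP 3.3 gives as the original target. The documents do not say whether 0.8 is a raw or a residual SD. If it is raw, the existing covariates may already lift power above 84%.

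Lateness is the weakest objection. SAP version 2.0 was itself opened in June 2017 to add by-gender models, and SAP 3.5.2 keeps the codes blinded until the SAP is approved and the Part A database is locked.

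**Conclusion.** A free improvement, low severity. The planned primary analysis is valid as written, with an unbiased contrast, intact type I error and a correct power statement. What can be said is that precision on the gatekeeping endpoint may be forgone, and that the only route by which age reaches PBVC depends on chance imbalance.

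It would go too far to say that precision is being given away. That needs an age–PBVC association which the documents do not supply. The premise that brain volume loss depends on age has no source in them and is not relied on here.

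The size runs from no gain to about 3.5 power points at the top of the assumed range, equivalent to 14 more evaluable patients per arm. It rests on the assumed R², on 0.8 being the residual SD, and on 126 evaluable patients per arm. The recommendation does not depend on where in that range the truth lies, because the cost at zero is one degree of freedom.

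**What to change.** Before unblinding:

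1. Add AGE (continuous, at baseline) unconditionally to the text and MODEL statement of SAP 7.2, keeping every other term.
2. Add the same term to the matching PBVC model in SAP 7.5.21.
3. Record the change in SAP section 12, since Protocol 9.6.4.1 carries the list without age. The SAP preface already says that the SAP prevails where the two differ.
4. Remove age from the conditional list in SAP 7.3, where it would be redundant.

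The cost is one term in text and code and one degree of freedom. No new data are needed. If the sponsor prefers to leave age out, one sentence giving the reason would settle the point.
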